7.2. Secondary statistical analyses

7.3. Biomarker Analyses

7.3.1. Overview of Planned Biomarker Analyses

As per Primary Analysis, see Section [7.1](#), but for secondary comparisons detailed in [Figure 1](#).

8. SAFETY ANALYSES

The safety analyses will be based on the Safety population, unless otherwise specified.

8.1. Adverse Events Analyses

Adverse events analyses including the analysis of adverse events (AEs), Serious (SAEs) and other significant AEs will be based on GSK Core Data Standards. The details of the planned displays are provided in [Appendix 10: List of Data Displays](#)

8.2. Clinical Laboratory Analyses

Laboratory evaluations including the analyses of Chemistry laboratory tests, Hematology laboratory tests, Urinalysis, and liver function tests will be based on GSK Core Data Standards. The details of the planned displays are in [Appendix 10: List of Data Displays](#).

8.3. Other Safety Analyses

The analyses of non-laboratory safety test results and vital signs will be based on GSK Core Data Standards, unless otherwise specified. The details of the planned

8.3.1. Interim Analysis 1

No formal safety analyses will be produced for the interim analysis.

8.3.2. Interim Analysis 2

No formal safety analyses will be produced for the interim analysis.

10. APPENDICES

10.1. Appendix 1: Protocol Deviation Management and Definitions for Per Protocol Population

10.1.1. Exclusions from Per Protocol Population

A subject meeting any of the following criteria will be excluded from the Per Protocol population:

Number	Exclusion Description
01	Eligibility criteria not met
02	Excluded medication, vaccine or device
03	Equipment procedures
04	Biological sample specimen procedures

10.2. Appendix 2: Schedule of Activities

10.2.1. Protocol Defined Time & Events

Screening procedures in addition to those listed below are (outpatient visit): Informed consent; Inclusion / Exclusion criteria; demography.

Procedure	Screening (between - 56 to 7 days prior to study session)	Study Session Day 1			Telephone follow-up Day ~2 to ~ Day 4	Telephone follow-up Day ~7 to Day ~14	Notes
		Pre biopsy	Biopsy	End of study session visit			
Full physical exam	X						To be completed if a post study visit is required. Attendance to the unit post study sessions only if necessary (at discretion of investigator)
Medical history / Past and current medical conditions	X	X					To be completed if a post study visit is required. Attendance to the unit post study sessions only if necessary (at discretion of investigator)

Procedure	Screening (between - 56 to 7 days prior to study session)	Study Session Day 1			Telephone follow-up Day ~2 to ~ Day 4	Telephone follow-up Day ~7 to Day ~14	Notes
		Pre biopsy	Biopsy	End of study session visit			
Laboratory assessments	X ¹	X ²					To be completed if a post study visit is required. Attendance to the unit post study sessions only if necessary (at discretion of investigator). 1. Blood testing in fasted condition at screening 2. Haematology and clinical chemistry only on Day 1 in a non fasted condition
Concomitant medication review	X	X			X	X	
Alcohol Urine Test and Test for Drugs of Abuse	X	X					
Urine Pregnancy test (in women of child bearing potential)	X	X					

CONFIDENTIAL

203158

Procedure	Screening (between - 56 to 7 days prior to study session)	Study Session Day 1			Telephone follow-up Day ~2 to ~ Day 4	Telephone follow-up Day ~7 to Day ~14	Notes
		Pre biopsy	Biopsy	End of study session visit			
Vital signs	X	X		X			To be completed if a post study visit is required. Attendance to the unit post study sessions only if necessary (at discretion of investigator)
Proposed biopsy site review		X					
Peripheral blood collection for cell isolation		X					
Peripheral blood collection for genetics		X					Optional in consenting subjects
Inguinal lymph node biopsy (fine needle aspirate & core biopsy)			X				
Wound assessment				X	X (telephone)	X (telephone)	To be completed if a post study visit is required. Attendance to the unit post study sessions only if necessary (at discretion of investigator)

CONFIDENTIAL

203158

Procedure	Screening (between - 56 to 7 days prior to study session)	Study Session Day 1			Telephone follow-up Day ~2 to ~ Day 4	Telephone follow-up Day ~7 to Day ~14	Notes
		Pre biopsy	Biopsy	End of study session visit			
Pre- & post-biopsy questionnaire to assess subject experience of lymph node biopsy		X			X (fill in questionnaire on the day after the procedure, communicate answers via telephone a few days after)		
SAE review		←-----→					
AE review		←-----→					

10.3. Appendix 3: Data Display Standards & Handling Conventions

10.3.1. Reporting Process

Software	

 The currently supported versions of SAS software will be used. 	
Reporting Area	
HARP Server	: uk1salx00175
HARP Compound	: \\arprod\\nocompound\\mid203158 \\arwork\\nocompound\\mid203158
Analysis Datasets	

 Analysis datasets will be created according to Legacy GSK A&R dataset standards. 	
Generation of RTF Files	

 RTF files will be generated for the final analysis tables only. 	

10.3.2. Reporting Standards

General	

 The current GSK Integrated Data Standards Library (IDSL) will be applied for reporting, unless otherwise stated: 
 4.03 to 4.23: General Principles 5.01 to 5.08: Principles Related to Data Listings 6.01 to 6.11: Principles Related to Summary Tables 7.01 to 7.13: Principles Related to Graphics 	
Formats	
	
 GSK IDSL Statistical Principles (5.03 & 6.06.3) for decimal places (DP's) will be adopted for reporting of data based on the raw data collected. Numeric data will be reported at the precision collected on the eCRF. The reported precision from non eCRF sources will follow the IDSL statistical principles but may be adjusted to a clinically interpretable number of DP's.
Planned and Actual Time	
	
 Reporting for tables, figures and formal statistical analyses: 
 Planned time will be used in figures, summaries, statistical analyses and calculation of any derived parameters, unless otherwise stated. The impact of any major deviation from the planned assessment times and/or scheduled visit days on the analyses and interpretation of the results will be assessed as appropriate. Reporting for Data Listings: 
 Planned and actual time will be shown in listings (Refer to IDSL Statistical Principle 5.05.1). Unscheduled or unplanned readings will be presented within the subject's listings.

Unscheduled Visits	

• Unscheduled visits will not be included in summary tables.• Unscheduled visits will not be included in figures.• All unscheduled visits will be included in listings.	
Descriptive Summary Statistics	
Continuous Data	Refer to IDSL Statistical Principle 6.06.1
Categorical Data	N, n, frequency, %

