6.1. Time and Events Table

T1D

Diagnosis (N.B. "T1D diagnosis" is not applicable to healthy volunteers)

Screening procedures in addition to those listed below are (outpatient visit): Informed consent; Inclusion / Exclusion criteria; demography.

Procedure	Screening (between -56 to 7 days prior to study session)	Study Session Day 1			Telephone follow-up Day ~2 to ~ Day 4	Telephone follow-up Day ~7 to Day ~14	Notes
		Pre biopsy	Biopsy	End of study session visit			
Full physical exam	X						To be completed if a post study visit is required. Attendance to the unit post study sessions only if necessary (at discretion of investigator)
Medical history / Past and current medical conditions	X	X					To be completed if a post study visit is required. Attendance to the unit post study sessions only if necessary (at discretion of investigator)

Procedure	Screening (between -56 to 7 days prior to study session)	Study Session Day 1			Telephone follow-up Day ~2 to ~ Day 4	Telephone follow-up Day ~7 to Day ~14	Notes
		Pre biopsy	Biopsy	End of study session visit			
Laboratory assessments (see Section 6.7.5)	X ¹	X ²					To be completed if a post study visit is required. Attendance to the unit post study sessions only if necessary (at discretion of investigator) 
 1. Blood testing in fasted condition at screening 2. Haematology and clinical chemistry only on Day 1 in a non fasted condition
Concomitant medication review	X	X			X	X	
Alcohol Urine Test and Test for Drugs of Abuse	X	X					
Urine Pregnancy test (in women of child bearing potential)	X	X					

Procedure	Screening (between -56 to 7 days prior to study session)	Study Session Day 1			Telephone follow-up Day ~2 to ~ Day 4	Telephone follow-up Day ~7 to Day ~14	Notes
		Pre biopsy	Biopsy	End of study session visit			
Vital signs	X	X		X			To be completed if a post study visit is required. Attendance to the unit post study sessions only if necessary (at discretion of investigator)
Proposed biopsy site review		X					
Peripheral blood collection for cell isolation		X					
Peripheral blood collection for genetics		X					Optional in consenting subjects
Inguinal lymph node biopsy (fine needle aspirate & core biopsy)			X				
Wound assessment				X	X (telephone)	X (telephone)	To be completed if a post study visit is required. Attendance to the unit post study sessions only if necessary (at discretion of investigator)

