6.6. Wound assessment

A visual assessment of the LN biopsy site will be conducted by the investigator before the end of the study visit to ensure adequate haemostasis and wound management. A sterile adhesive dressing will be applied to the wound. Subjects will be asked to contact the investigator for an examination if they report any signs or symptoms related to persistent pain in the biopsy area or signs or symptoms indicating infection.

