5.2. Baseline Definitions

For all endpoints, the baseline value will be the latest pre-biopsy assessment with a non-missing value, including those from unscheduled visits. If time is not collected, Day 1 assessments are assumed to be taken prior to biopsy and used as baseline.

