10.4. Appendix 4: Derived and Transformed Data

10.4.1. General

Multiple Measurements at One Time Point

 Mean of the measurements will be calculated and used in any derivation of summary statistics but if listed, all data will be presented. Subjects having both High and Low values for Normal Ranges at any post-baseline visits for safety parameters will be counted in both the High and Low categories of “Any visit post-baseline” row of related summary tables. This will also be applicable to relevant Potential Clinical Importance summary tables.
Study Day

 Calculated as the number of days from date of biopsy : 
 Ref Date = Missing → Study Day = Missing Ref Date < Biopsy Date → Study Day = Ref Date – Biopsy Date Ref Date ≥ Biopsy Date → Study Day = Ref Date – (Biopsy Date) + 1

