10.10.6. Safety Tables

Safety : Tables					
No.	Population	IDSL / TST ID / Example Shell	Title	Programming Notes	Deliverable [Priority]
Adverse Events (AEs)					
3.01	Safety	AE1	Summary of Adverse Events Summary by SOC and PT		SAC
3.02	Safety	AE15	Summary of Common (>=5% incidence) Non-Serious Adverse Events by SOC and PT (No. of Subjects and occurrences)		SAC
3.03	Safety	AE5A	Summary of All Adverse Events by Maximum Intensity by System Organ Class and Preferred Term		SAC
Serious Adverse Events					
3.04	Safety	AE16	Summary of Serious Adverse Events by SOC and PT (No. of Subjects and occurrences)		SAC
3.05	Safety	AE1	Summary of Adverse Events Leading to Withdrawal from Study by SOC and PT		SAC
Vital Signs					
3.06	Safety	VS1	Summary of change from baseline in Vital Signs		SAC
3.07	Safety	VS7	Summary of Vital Sign Results Relative to Potential Clinical Importance (PCI) Criteria Post- Baseline Relative to Baseline		SAC

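### Vital signs taken at discretionary post-biopsy visits would naturally fall outside Tables 3.06 and 3.07, because the final SAP keeps unscheduled visits out of summary tables without exception

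*SAP*

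**What the plan says.** The SAP document holds two plans, one for the second interim analysis and one for the final report. In the final plan, 10.3.2 Reporting Standards says "Unscheduled visits will not be included in summary tables", applies the same exclusion to figures, and then says "All unscheduled visits will be included in listings". It carves out nothing for safety or PCI tables. The interim plan has the same exclusion in its 10.3.3.

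The schedule (Protocol 6.1, repeated in final SAP 10.2.1) places vital signs at screening, before the biopsy on Day 1, and at the end of the Day 1 session. Both later contacts are telephone calls with no vital signs. The vital-signs row carries a note: "Vital signs X X X To be completed if a post study visit is required". Protocol 6.1 adds: "Attendance to the unit post study sessions only if necessary (at discretion of investigator".

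Final SAP 10.10.6 lists two vital-sign tables: 3.06 (change from baseline) and 3.07, "Summary of Vital Sign Results Relative to Potential Clinical Importance (PCI) Criteria Post- Baseline Relative to Baseline". The programming-notes column is empty for both.

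Final SAP 10.4.1 says that a subject with both high and low values after baseline is counted in both categories of the *Any visit post-baseline* row, and continues: "This will also be applicable to relevant Potential Clinical Importance summary tables". Final SAP 5.2 takes as baseline the latest non-missing pre-biopsy value, "including those from unscheduled visits".

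**The concern.** The protocol foresees that a subject may be seen again after the biopsy and asks for vital signs when that happens. Protocol 6.6 gives the kind of occasion: "Subjects will be asked to contact the investigator for an examination if they report any signs or symptoms related to persistent pain"; it also names signs of infection. If such a visit counts as unscheduled, its blood pressure and pulse are collected and listed but cannot reach either vital-sign table.

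At stake is how complete Table 3.07 is. A subject whose only value of potential clinical importance occurs at a post-study visit would count in the table as having none, although the listings would show the value. Table and listing could then disagree on who had such a value, in a study where safety and tolerability of the biopsy is a secondary objective.

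**Working it through.** The plan states no figure to reproduce. The check is a trace of which readings can reach the tables.

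**Step 1. Place each time point against the rule in final SAP 10.3.2.**

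| Time point | Vital signs | Relative to biopsy | Can enter Tables 3.06/3.07 after baseline? |
|---|---|---|---|
| Screening | scheduled | before | no, baseline side only |
| Day 1, pre-biopsy | scheduled | before | no, baseline side only |
| Day 1, end of session | scheduled | after | yes |
| Telephone, about Day 2 to 4 | none | after | nothing to enter |
| Telephone, about Day 7 to 14 | none | after | nothing to enter |
| Post-study visit, if held | if required | after | no, if treated as unscheduled |

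Scheduled time points: 3. Less the 2 before biopsy: 3 − 2 = 1 scheduled post-baseline reading.

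**Step 2. Is the post-study visit unscheduled?** Neither plan defines the term. The visit appears only as a note, is discretionary, and has no column, day or window. Final SAP 10.3.2 also says summaries use planned time, and this visit has none. Treating it as unscheduled is an inference, but the natural one.

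**Step 3. Does anything override the rule?** The programming notes for Tables 3.06 and 3.07 are empty, and 10.3.2 has no exception. Protocol 6.7 allows safety time points to be added during the study, but the current schedule has none.

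**Step 4. What is left for the any-visit row?** With one admissible post-baseline time point, and repeat measurements at a time point averaged for summaries (final SAP 10.4.1), a subject cannot be both high and low on an absolute criterion. The row then equals the end-of-session row, and the double-counting convention has nothing to act on for those criteria.

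**Step 5. Scale, for illustration only.** Assume 15 subjects per group with post-biopsy vital signs, and one whose only PCI value came at a post-study visit. Table 3.07 would then be short by 1/15 = 6.7 percentage points in that group, or 1/30 = 3.3 points overall. Neither the 15 nor the one subject is given for this table. Fifteen is the maximum number of evaluable subjects per group, whereas the table uses the Safety population, meaning everyone who completes any study assessment.

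**The case against.** **The visit may not be unscheduled at all.** The Time and Events table itself provides for it, so a data manager could map it as its own visit. That is fair. The documents support *naturally treated as unscheduled*, not *by definition unscheduled*. But if the sponsor means to include these visits, the SAP does not say so.

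**The safety question is answered elsewhere.** The stated safety endpoint is the number of AEs and SAEs after the biopsy, not vital signs. An infection or bleed that led to a visit would be recorded as an AE, and Protocol 11.3.1 counts vital signs judged clinically significant as AEs. Tables 3.01 to 3.04 carry no visit restriction. Listings 19 and 20 keep the readings. All of this stands and limits the point to a minor one.

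**The table's layout cannot be seen.** Table 3.07 follows a standard shell (VS7), and the final SAP makes display specifications available only on request. Whether the shell has an any-visit row cannot be checked. The exclusion in 10.3.2 would still govern which readings feed that row.

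**Two further faults that a reader might infer.** One is that 10.3.2 contradicts 10.4.1. It does not: 10.4.1 says how to count a subject with both high and low values, not which visits qualify. Under 10.3.2 the row is redundant, not contradictory. The other is that the rules are one-sided because 5.2 admits unscheduled readings as baseline. The two rules do different jobs: 5.2 chooses a reference value, while 10.3.2 decides which visits a table displays. Neither inference is supported.

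**Conclusion.** As written, 10.3.2 most naturally confines the post-baseline side of Tables 3.06 and 3.07 to the single end-of-session reading, leaving out the later vital signs that the protocol itself asks for. This rests on two assumptions: that post-study visits are handled as unscheduled, and that no time points are added under Protocol 6.7.

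The consequence is small: a descriptive secondary safety display in an exploratory study may understate PCI values after biopsy. By how much is unknown, because no rate is given for post-study visits or for PCI values at them.

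A reader might infer that complications would vanish from the safety reporting, or that the omitted readings are the most abnormal ones. The documents support neither. The AE tables and listings remain, and the triggers named in Protocol 6.6 are pain and signs of infection. The PCI criteria in final SAP 10.6.2 cover blood pressure and heart rate but not temperature, so fever alone would not change Table 3.07. The illustrative percentages should likewise not be read as an estimate of bias.

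**What to change.** In final SAP 10.3.2, after the sentence excluding unscheduled visits from summary tables, add: *except that all post-biopsy vital-sign values, scheduled or unscheduled (including post-study visits), count in the Any visit post-baseline row of the PCI table (3.07)*. Repeat this in the empty programming note for Table 3.07, so that the row is produced whatever the standard shell contains. Leave by-visit rows unchanged. A separate post-study-visit row in Table 3.06 is optional.

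The cost is one sentence and a programming note, with no new data. The PCI percentages may be slightly less favourable. In return, Table 3.07 would agree with Listing 20 on who had such a value after biopsy, and the any-visit row would have a purpose.

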10.4. Appendix 4: Derived and Transformed Data

10.4.1. General

Multiple Measurements at One Time Point

 Mean of the measurements will be calculated and used in any derivation of summary statistics but if listed, all data will be presented. Subjects having both High and Low values for Normal Ranges at any post-baseline visits for safety parameters will be counted in both the High and Low categories of “Any visit post-baseline” row of related summary tables. This will also be applicable to relevant Potential Clinical Importance summary tables.
Study Day

 Calculated as the number of days from date of biopsy : 
 Ref Date = Missing → Study Day = Missing Ref Date < Biopsy Date → Study Day = Ref Date – Biopsy Date Ref Date ≥ Biopsy Date → Study Day = Ref Date – (Biopsy Date) + 1

10.4.2. Study Population

Age

 GSK standard IDSL algorithms will be used for calculating age where birth date will be imputed as follows: 
 Any subject with a missing date and month will have this imputed as ‘30th June’. The date of final screening will be used as the reference for the calculation. Birth date will be presented in listings as ‘YYYY’.
Body Mass Index (BMI)

 Calculated as Weight (kg) / [Height (m)]²

10.4.3. Safety

Laboratory Parameters

 If a laboratory value which is expected to have a numeric value for summary purposes, has a non-detectable level reported in the database, where the numeric value is missing, but typically a character value starting with ‘<x’ or ‘>x’ (or indicated as less than x or greater than x in the comment field) is present, will be imputed using the following rules: 
 If value is below limit of quantification, then 0.5*lower limit of quantification will be used If the value is above upper limit of quantification, then the upper limit of quantification will be used.

10.5. Appendix 5: Premature Withdrawals & Handling of Missing Data

10.5.1. Premature Withdrawals

Element	Reporting Detail
General	
 Subject study completion (i.e. as specified in the protocol) was defined as one who has completed all phases of the study including the follow-up call(s). The end of the study is defined as the last subject's last telephone call. As defined in the protocol the overall study duration for each subject will be up to 8 weeks, including the screening period. Withdrawn subjects may be replaced in the study. All available data from subjects who were withdrawn from the study will be listed and all available planned data will be included in displays, unless otherwise specified.

10.5.2. Handling of Missing Data

Element	Reporting Detail
General	
 Missing data occurs when any requested data is not provided, leading to blank fields on the collection instrument: 
 These data will be indicated using a "blank" in subject listing displays. Unless all data for a specific visit are missing in which case the data is excluded from the listing. Answers such as "Not applicable" and "Not evaluable" are not considered to be missing data and should be displayed as such.
Outliers	
 Any subjects excluded from the summaries and/or statistical analyses will be documented along with the reason for exclusion in the clinical study report.

10.5.2.1. Handling of Missing Dates

Completely missing dates will remain missing, with no imputation applied.

10.5.2.2. Handling of Partial Dates

Element	Reporting Detail
Concomitant Medications	
 Partial dates for any concomitant medications recorded in the CRF will be imputed using the following convention: 
 If the partial date is a start date, a '01' will be used for the day and 'Jan' will be used for the month If the partial date is a stop date, a '28/29/30/31' will be used for the day (dependent on the month and year) and 'Dec' will be used for the month. The recorded partial date will be displayed in listings.

Element	Reporting Detail
Adverse Events	
Any partial dates for adverse events will be raised to data management. If the full date cannot be ascertained, the following assumptions will be made:
If the partial date is a start date, a '01' will be used for the day and 'Jan' will be used for the month.However, if these results in a date prior to day of biopsy and the event could possibly have occurred post-biopsy from the partial information, then the biopsy date will be assumed to be the start date.The AE will then be considered to start post-biopsy (worst case).If the partial date is a stop date, a '28/29/30/31' will be used for the day (dependent on the month and year) and 'Dec' will be used for the month.The recorded partial date will be displayed in listings.

